1. OBJECTIVES

1.1 Primary Objective

It has been shown that exemestane reduces estradiol levels both at the standard dose (25 mg/day) and at lower doses. We expect to achieve with 25 mg three times a week and 25 mg/week similar effects in estradiol reductions to the standard dose of 25 mg daily.

Non-inferiority of percent change in time of serum estradiol levels, adjusted for baseline levels, following four up to six weeks of exemestane 25 mg given three times per week or one time per week compared with exemestane 25 mg daily dosing.

1.2 Secondary Objectives

Secondary objectives are:

- To assess safety and toxicity.
- To support the preventive activity of exemestane we will investigate the change in Ki-67 and PgR levels in tumor cells and the adjacent intraepithelial neoplasia or benign histologic structures.
- To assess possible association of estradiol level with tissue and circulating biomarkers.
- To investigate possible pharmacogenetic markers.
- To assess drug levels on tissue samples.
- To investigate tissue and circulating proteomics profiling.

2. BACKGROUND

2.1 Breast Cancer

Breast cancer is the most common cancer in women and its incidence is rapidly increasing, largely because of an ageing population and several lifestyle changes, such as decreases in physical activity, increase in obesity, later age at first childbirth, and reductions in breastfeeding. Estrogen is a key factor in breast cancer carcinogenesis, and reductions in its synthesis can decrease breast cancer risk. Estrogen production is driven by the aromatase enzyme, which converts androgens to estrogens. Trials in the adjuvant setting have shown that aromatase inhibitors effectively prevent breast cancer recurrence (1) and breast cancer events in at-risk women (2,3).

The pre-surgical - window of opportunity - trial design has been successfully used to streamline drug development, check tumor sensitivity to a given drug and shape up new preventive strategies (4). The change in Ki-67 labeling index is considered an appropriate endpoint biomarker for preoperative studies (5,6). The post-treatment tumor expression of Ki-67 has been shown to be correlated with disease-free survival and overall survival (7). In addition the Ki-67 analysis on adjacent IEN or atypical hyperplasia can assess the potential preventive activity of the tested agent (8,9).

2.2 Exemestane

Exemestane is an irreversible aromatase inhibitor. This drug is highly specific and inhibits peripheral conversion of androstenedione to estrogen down to 98%. The drug was recently approved for the adjuvant setting, and the placebo-controlled phase III MAP.3 chemoprevention trial showed an overall 65% reduction in breast cancers and a specific ER-positive breast cancer reduction of 73% in the intervention arm compared to the placebo group (3).

Exemestane is in fact a steroidal aromatase inactivator with a long-lasting effect attributable to a tight covalent binding to the enzyme. The estradiol suppression persists for at least 5 days after administration of a single dose (10). This suggests, especially in a prevention setting, the possibility to reduce the dose and change the time schedule, while still maintaining a significant estradiol reduction. A study of 10 patients found that women who took a daily dose of 10 mg of exemestane achieved equivalent estradiol suppression as women who took a dose of 25 mg daily (11).

The exemestane steroidal structure suggests it may have androgenic properties that could potentially counteract any anti-estrogenic properties in bone and possibly sexual function and menopausal symptoms. The favorable profile on bone may represent an advantage of this agent in prevention settings in unaffected women at increased risk for breast cancer.

2.3 Rationale

Despite the strong positive findings in breast cancer prevention with tamoxifen, the attitude towards chemoprevention remains ambivalent, and the associated side effects hamper the drug uptake by high-risk women who could benefit from its preventive effects.

Among the strategies to overcome tamoxifen side effects, we have intensively investigated alternative low doses of tamoxifen in several phase II studies (12-14), and in two phase III studies (15,16).

More recently AIs have proven their capability to lower cancer incidence in high risk women. The Mammary Protocol 3 (MAP.3) trial (3) was a randomized, placebo-controlled, double-blind trial of exemestane 25 mg/day administered to postmenopausal women 35 years or older with at least one of the following risk factors: 60 years or older; Gail 5-year risk score greater than 1.66%; prior atypical ductal or lobular hyperplasia or LCIS; or DCIS with mastectomy. A total of 4,560 women (median age 62.5 years, median Gail risk score 2.3%) were randomly assigned to either exemestane or placebo. At a median follow-up of 35 months, 11 invasive breast cancers were detected in those given exemestane and 32 in those given placebo, with a 65% relative reduction in the annual incidence of invasive breast cancer (0.19% vs 0.55%; HR 0.35, 95% CI 0.18-0.70; $p = 0.002$).

The IBIS II Prevention trial included 1,920 women randomly assigned to receive anastrozole 1 mg daily and 1,944 assigned to placebo. After a median follow-up of 5 years, 2% of women in the anastrozole group vs. 4% in the placebo group have developed breast cancer (HR 0.47 95% CI 0.32, 0.68; $p < 0.0001$). The predicted cumulative incidence of all breast cancers after 7 years has been 5.6% in the placebo group and 2.8% in the anastrozole group (2). Musculoskeletal adverse events were common in the anastrozole group, but mostly of moderate severity. Vasomotor symptoms were common in both groups but the incidence was higher in women on anastrozole. No increases in fractures, myocardial infarction, or cardiac failure were observed between the groups.

However we might expect that an AI would achieve low acceptability similar to the SERMs by high risk women for the undesirable symptoms, bone density loss, musculoskeletal ache, climacteric syndrome, and ultimate possible impact on QoL, significantly compromising their motivation and adherence to a preventive treatment. Therefore, a significant step forward to promote breast cancer prevention in postmenopausal women is to ameliorate QoL issues by seeking for the minimally active AI dose and an intermittent schedule. A lighter schedule, compared to the standard regimen, may be much more appealing to a healthy at-risk woman.

For this purpose we are proposing a pre-surgical phase IIb, randomized, double-blind, multi-center study for postmenopausal women with histologically confirmed ER-positive breast cancer (Stage 0-II) comparing the exemestane standard daily dose regimen versus two alternative, less frequent dose regimens.

Rationale for Biomarkers

Estradiol: Overall, a strong positive association between breast cancer risk and circulating levels of

estrogens is now well confirmed among postmenopausal women; the top 20% hormone levels versus bottom 20% have a two- to three-fold higher risk of breast cancer (17). Interestingly, circulating estradiol levels can predict risk of hormone receptor positive breast cancer for up to 16-20 years. Top versus bottom quartile contrast RR was 2.0 (95% CI: 1.4-2.7; p trend<0.001) for <10 years, 2.0 (95%CI: 1.3-3.1; p trend=0.002) for >10-20 years before diagnosis (18).

The direct consequence of AIs in postmenopausal women is a steep decrease in circulating estrogens and their metabolites. For the assessment of exemestane activity at different doses and schedules the most appropriate biomarker appears to be circulating estradiol concentrations (19-21). In postmenopausal women, estradiol levels are low and their assessment is technically challenging as routine labs generally lack standardized sensitive methods. During estrogen suppression with AIs for breast cancer treatment and prevention, the accuracy of estradiol assay becomes of paramount importance as plasma levels are very low (<5 pmol/L). Liquid chromatography coupled with tandem mass spectrometry (LC-MS/MS) provides greater sensitivity and specificity than radio immunoassays (RIA).

Ki-67: Several studies indicate that staining with the Ki-67 antibody may be useful in monitoring response to anti-estrogen therapy. We previously conducted a presurgical trial assessing tamoxifen dose escalation. Our study showed that the effects of tamoxifen on breast cancer cell proliferation, as assessed by the change in the percentage of cells expressing Ki-67, was comparable among women who received a daily tamoxifen dose of 1 mg, 5 mg, or 20 mg administered for 4 weeks (22). These results led us to focus on low dose tamoxifen in several chemoprevention trials. Ki-67 proliferation index has hence increasingly been used as a surrogate endpoint. Additional evidences from neoadjuvant trials pointed to a prognostic value of Ki-67. Measurements of tumor Ki-67 level after only 2 weeks treatment with either tamoxifen or anastrozole or their combination improved the prediction of recurrence-free survival over baseline Ki-67 after a median of 3 years in postmenopausal women (6,23).

Our findings on standard and low dose tamoxifen confirmed this observation, Ki-67 expression after 4 weeks of tamoxifen predicted recurrence-free and overall survival significantly better than baseline Ki-67. Post-tamoxifen Ki-67 point increase predicted a 5% significant increased risk of breast cancer recurrence. Likewise, overall mortality, mostly due to breast cancer, was better predicted by post-tamoxifen Ki-67 (7).

More recently, we conducted a WOP trial in postmenopausal women with exemestane (25 mg/day) demonstrating a significant reduction in Ki-67 (a 10 point decrease) without any significant toxicity(24). To support the hypothesis of an alternative dose, the Ki-67 was reduced at the same extent irrespective of time since last drug intake (≤ 24 hours or >24 hours) and serum concentrations of exemestane (10 nM vs 2 nM), according to time since last drug intake (25).

Progesterone Receptor (PgR): Compared to Ki-67 the role of PgR is less clear, at least with tamoxifen treatment (26). Its modulation by tamoxifen is controversial, some studies showed no significant effect on PgR expression. In a low percentage of participants a decreased expression after short tamoxifen treatment has been observed, and these participants showed a worse response to the treatment, but the data were more informative if both pre and post treatment PgR expression was taken into account (27). Moreover, this receptor may change in time also with no treatment. Similarly to Ki-67 exemestane can significantly reduce PgR expression after 6 weeks of treatment (24). It will be useful to compare the modulating effect by exemestane dose and eventually correlate it to Ki-67 changes.

Sex Hormones: Similarly to estradiol, other circulating sex hormones are involved in breast carcinogenesis, and their analysis can contribute to a better understanding of their role in the tumor pathogenesis and drug efficacy through their modulation. Among postmenopausal women, higher levels of endogenous sex hormones and lower levels of sex hormone binding globulin (SHBG) are associated with increased risk of breast cancer. Literature data clearly show the AIs activity on these hormones is due to the direct enzyme inactivation. We have recently published data in premenopausal women that

showed in a multivariable analysis that SHBG had an HR = 2.26 (95 %CI 1.04-4.89) for the lowest versus the highest tertile (28). Endocrine effects of exemestane standard treatment in postmenopausal breast cancer patients result in suppression of estrone, estradiol and estrone sulfate and lowering of SHBG levels, and it increases testosterone, DHEAS and FSH levels. In this study it will be useful to compare the modulation of such hormones to evaluate the drug activity at different schedules. Their evaluation may help to understand the activity of the different proposed doses, and eventually provide an indication to response prediction (19,29,30).

Insulin – Insulin resistance: There is evidence of an association of androgen excess and insulin resistance, glucose intolerance and dyslipidemia in animal models as well as in women. Insulin resistance is considered an important feature of the metabolic syndrome, and is a risk factor for cardiovascular diseases, type 2 diabetes and cancer (31,32).

In aromatase deficient mice, in association with the increased levels of androgens, increased abdominal adiposity and higher insulin levels has been described. Several polymorphisms of the aromatase gene CYP19 (rs1008805, rs2446405 and rs2414096) are associated with increased risk for insulin sensitivity and diabetes in African Americans, Caucasians and Japanese(33). Based on these observations, we will measure insulin, glucose levels and insulin sensitivity (HOMA) to assess whether there is a different effect among the three exemestane doses.

Lipid profile: A concern with the use of aromatase inhibitors relates to an increased risk of cardiovascular events. It has been reported that, in postmenopausal women, the increase in cardiovascular risk may be ascribed to changes in lipid metabolism and, above all, to the elevation of low-density lipoprotein (LDL) cholesterol. Amongst aromatase inhibitors, exemestane may potentially have a more neutral effect on circulating lipid changes compared to letrozole and anastrozole. After 6 weeks treatment of exemestane (24), total and HDL cholesterol decreased by -10 mg/dL (IQR -21 to -2) and -7 mg/dL (IQR -14 to -2), respectively. Triglycerides were reduced by -8 mg/dL (IQR -28 to -9). Similar results were previously described, however associated with an increase in LDL-cholesterol(34,35). Based on these observations, we will measure total, LDL,HDL cholesterol and triglyceride levels to assess whether there is a different effect among the three exemestane doses.

Adipokines: In the global picture of breast carcinogenesis, adipose tissue has been shown to play an important role. In particular, two adipokines, leptin and adiponectin, have been studied as risk biomarkers for breast cancer associated with obesity in postmenopausal breast cancer patients. Leptin may influence breast cancer through enhancing expression of aromatase providing a link between body weight (adipose tissue), estrogen levels and the risk for breast cancer development as well as poor prognosis (36). Adiponectin appears to have anti-inflammatory, antiatherogenic, anti-angiogenic and anti-diabetic properties. Serum adiponectin levels are reduced in obese women and they increase after relevant weight loss. Low levels of adiponectin are also closely linked to insulin resistance and hyperinsulinemia, which were demonstrated to be positively associated with breast cancer risk (37).

In a few subjects, it has been reported that exemestane can reduce leptin plasma level (38); if this effect can be confirmed on a larger population it can be considered an additional activity and potential effect for cancer treatment as well as prevention.

Proteomics: Proteomic analyses have been studied, with varying success, to identify on breast cancer tissue an expression profiling in order to discover protein biomarkers/signatures suitable for: characterization and subtyping of tumors, early diagnosis, and both prognosis and prediction of outcome (39). This dataset will allow us to run spectra network analysis for protein identification and comprehensive characterization of post-translational modifications, in addition to the traditional database search approach. It will also allow us to further develop the spectra network analysis algorithm for higher

charged peptides using multiple fragmentation capability of the new Fusion Tribrid mass spectrometer in [name] Shared Resource for the Herbert Irving Comprehensive Cancer Center (HICCC) at CUMC (40,41).

UGT2B17: Exemestane and its major metabolite 17-dihydroexemestane are metabolized by UGT enzyme. UGT genetic variations play a role in altered 17-dihydroexemestane glucuronidation and overall exemestane metabolism. The prevalence of the polymorphic UGT2B17 whole-gene deletion is approximately 30% in Caucasians. In vitro studies UGT2B17 gene deletion correlates with a significant decrease of 17-dihydroexemestane excretion and consequently increasing circulating levels (42). This could reflect an increased exemestane activity. We have data from a pre-surgical study, consistent with these observations, showing a significant association of the UGT2B17 deletion with increased serum concentration of 17-dihydroexemestane (25). Interestingly, Ki-67 decreased equally irrespective of time since last drug intake supporting the rationale of testing differential drug schedules.

Crown-like structures: The potential links between obesity, inflammation, and aromatase expression are still unclear. In both dietary and genetic models of obesity, necrotic adipocytes surrounded by macrophages forming crown-like structures (CLS) in the mammary glands and visceral fat have been observed. The presence of CLS was associated with activation of NF- κ B and increased levels of proinflammatory mediators (TNF- α , IL-1 β , Cox-2), which were paralleled by elevated levels of aromatase expression and activity in the mammary gland and visceral fat of obese mice (43). These preclinical findings were further assessed in 30 women undergoing breast surgery (44). CLS of the breast (CLS-B) was found in nearly 50% (14 of 30) of patient samples. The severity of breast inflammation, defined as the CLS-B index, correlated with both body mass index ($P < 0.001$) and adipocyte size ($P = 0.01$). Increased NF- κ B binding activity and elevated aromatase expression and activity were found in the inflamed breast tissue of overweight and obese women.

3. SUMMARY OF STUDY PLAN

We will conduct a multicenter, pre-surgical double-blind non-inferiority phase IIb study in which participants will be randomized to receive either exemestane 25 mg/day or 25 mg/ three times a week or a single dose of 25 mg/week for a minimum of 4 up to 6 weeks.

A total of 180 post-menopausal women will be accrued; 60 per arm, enrolled in 35 months and treated for a minimum of 4 up to 6 weeks.

Participants will be histologically-confirmed ER-positive (ER $\geq 10\%$) primary breast cancer patients who are candidates for breast surgery. Postmenopausal women younger than 76 years of age with cT₀₋₂, cN₀₋₁, M_x or women with larger tumors who refuse neo-adjuvant therapy before surgery are eligible. No previous treatment for breast cancer is allowed.

Complete physical exam and safety lab tests will be performed at baseline and at end of treatment (28+1, 35+1, 42+1 days). Phone contact will occur at day 1 and a week before surgery (+3 days).

Biomarkers: blood samples will be collected at baseline and the end of treatment (fasting blood for biomarkers will be collected prior to randomization and either on the day of surgery or the day before; fasting is strongly recommended but is not mandated), tissue samples will be collected from the diagnostic or research biopsy and at the time of surgery.

Duration of study will be four years: 35 months for accrual, 4-6 weeks of treatment, and one year for biomarkers measurement.

4. PARTICIPANT SELECTION

4.1 Inclusion Criteria

4.1.1 Postmenopausal women (* postmenopausal: age ≥ 60 years, or amenorrhea ≥ 12 months, or bilateral oophorectomy, or - in women with hysterectomy only - FSH in the menopausal levels as per local institutional guidelines if < 60 years old) with histologically-confirmed ER-positive ($\geq 10\%$) primary breast cancer stage cT₀₋₂, cN₀₋₁, M_x. Women with larger tumors who refuse chemo and/or endocrine neoadjuvant therapy can be eligible.

4.1.2 ECOG performance status ≤ 1 (Karnofsky $\geq 70\%$; see Appendix A).

4.1.3 Participants must have normal organ and marrow function as defined below:

Leukocytes	$\geq 3,000/\text{microliter}$
Absolute neutrophil count	$\geq 1,500/\text{microliter}$
Platelets	$\geq 100,000/\text{microliter}$
Total bilirubin	$\leq 2 \times$ institutional ULN
AST (SGOT)/ALT (SGPT)	$\leq 1.5 \times$ institutional ULN
Serum creatinine	≤ 1.5 times institutional ULN

4.1.4 Ability to understand and the willingness to sign a written informed consent document.

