7. CLINICAL EVALUATIONS AND PROCEDURES

7.1 Schedule of Events

The possibility of taking part in a pre-surgical trial will be presented to incoming postmenopausal women with a highly suspicious palpable lesion or a newly diagnosed ER-positive DCIS or breast cancer. The baseline visit will be scheduled for interested potential participants after histological confirmation.

SCHEDULE OF EVENTS

Evaluation/ Procedure	Screening Visit ¹	Baseline Visit/ Registration (within 14 days prior to randomization)	Randomization	Phone call (Day 1)	Phone call (1 week +3 days prior to surgery) ²	Final Visit (Days 28+1, 35+1, or 42+1) ³	Surgery (Days 29, 36 or 43) ¹²
Screening Informed Consent	X						
Tru-cut biopsy (Eligibility ER + breast cancer)	X						
Informed Consent		X					
Assess eligibility		X					
Medical history		X					
Physical exam/ height/weight/vital signs		X				X ^{9,10}	
Tobacco / alcohol use assessment		X					
Fasting blood lab tests ⁴		X				X	
Blood lab tests that may not be fasting ⁵		X				X ¹⁰	
Fasting blood for biomarkers ⁶		X				X	
Tissue for biomarkers (FFPE blocks or slides)		X					X
Frozen tissue for biomarkers							X
Frozen tissue for proteomics ¹¹							X ¹¹
Concomitant medications		X			X	X	
Baseline symptoms		X					
Confirm eligibility		(X)	X				
Randomization			X				
Dispense study agent ¹³			X ¹³				
Treatment initiation				X ⁷			
Collect study agent						X	X
Compliance					X	X	
Review agent diary/record						X	
Adverse events					X	X	
QoL questionnaire ⁸		X				X	

¹ For the Italian sites only

² If the participant is seen on site for the physical exam and blood safety tests on Day 7 prior to surgery, perform all procedures in person rather than as a phone call. In all other cases call the participant on the phone 1 week +3 days prior to surgery

³ Based on institutional procedure, the final visit may occur on the same day as surgery or the day before. The Final Visit must be

conducted on Days 28+1, 35+1, or 42+1.

⁴ **Fasting** blood lab tests (local lab): Glucose, total cholesterol, HDL cholesterol and triglycerides. Fasting is strongly recommended, but is not mandated. Every effort should be taken to draw these labs fasting.

⁵ Blood tests for safety that do not require fasting: complete blood count (CBC), AST, ALT, Na, K, BUN, total bilirubin, Cl, Ca, alkaline phosphatase, creatinine, and FSH if needed

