10.3 Shipping Instructions

In order to keep shipping costs at an affordable level, Participating Centers are requested to store blood samples at -80°C until pick-up by a courier will be arranged by and to the Central Laboratory at the Division of Cancer Prevention and Genetics, European Institute of Oncology in Milan, Italy. Samples will be shipped on dry ice in compliance with the International Air Transport Association (IATA) Dangerous Goods Regulations. Specific instructions about specimen shipping will be provided in a dedicated Manual of Operations and Procedures.

Tissue specimens will be stored locally until shipment the Central Laboratory at the Division of Cancer

Prevention and Genetics, European Institute of Oncology in Milan, Italy. Storage and shipment instructions are outlined in the Manual of Operations and Procedures.

Note to the US Sites: Tissue collected for Proteomic Biomarker Discovery will be stored locally and shipped to the Proteomics Shared Resource, Herbert Irving Comprehensive Cancer Center, Columbia University Medical Center. Storage and shipment instructions are outlined in the Manual of Operations and Procedures.

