13.4 Primary Objective, Endpoint(s), Analysis Plan

Primary objective and primary endpoint

Since the primary objective of this study is to assess if the reduction in estradiol with the standard dose is comparable with the other lower doses, we will measure the estradiol before and after treatment. Thus, the primary endpoint is the percentage change of serum estradiol concentration from baseline and we will compare the median change and percentage changes among arms.

We choose the percentage change as the primary endpoint because it will improve generalization of results, given the wide variability among different assays, and because we predict that a large percentage of participants will have the final values of estradiol below the detectable level.

Analysis plan

We will present full distribution and median values of estradiol at baseline (before treatment), at post (after treatment), and changes and percentage changes (with interquartile ranges) of estradiol level, from baseline to post, by arms. Differences by arms of % change, change and final values will be tested considering t-test and ANCOVA models. Estradiol at baseline will be included as explanatory variable together with other possible confounders such as BMI, age and time since last dose. Normal distribution of residuals from full model will be checked and, if needed, a transformation will be considered.

We will also compare percentages of participants with final values of estradiol below the detectable level by arms with Chi-square tests and logistic models.

We will carry out the two comparisons with the standard dose considering $\alpha=0.025$.

Power analysis

Given the expected reduction of at least 80% change with exemestane at 25 mg daily (56) considered as reference group (control arm) against 25 mg 3 times a week, or 25 mg weekly, for the power calculation we assume a non-inferiority difference of 6% in percentage changes of estradiol after treatment from baseline, using a one-sided, two-sample t-test. A total sample size of 162 participants (54 participants per arm), enables us to achieve 80% power with a margin of equivalence of -6% in the mean percentage changes from baseline at the lower dose compared to the standard dose. The true difference between the means percentage changes is assumed to be 0.0%.

The significance level of the test is 0.025 to take into account of multiple comparisons (we will compare the changes at the two low doses with the standard dose)(57).

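### Section 4.1.1: the amenorrhea route, read literally, lets women under 60 with hysterectomy only bypass the FSH result that the same sentence requires of them

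*Combined protocol and SAP*

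**What the plan says.** Section 4.1.1 of the combined protocol and SAP gives four routes to postmenopausal status, joined by the word or. Three come first: "postmenopausal: age ≥ 60 years, or amenorrhea ≥ 12 months, or bilateral oophorectomy". The fourth applies to women who have had a hysterectomy only: "FSH in the menopausal levels as per local institutional guidelines if < 60 years old". The amenorrhea route, which stands in the list as "amenorrhea ≥ 12 months, or bilateral oophorectomy, or - in women with hysterectomy only - FSH in the menopausal levels", carries no condition on cause, intact uterus or age.

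FSH appears in two other places, footnote 5 of the schedule of events (section 7.1) and the baseline tests in section 7.3, both times in the form "creatinine, and FSH if needed". Neither says what makes it needed.

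Section 3 sets an upper age limit only ("Postmenopausal women younger than 76 years of age"). None of the exclusions in section 4.2 concerns ovarian function. Serum for estradiol is drawn at baseline, but under section 10.3 "Participating Centers are requested to store blood samples at -80°C until pick-up by a courier", and no eligibility rule uses the result.

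**The concern.** By naming an FSH result for women under 60 with hysterectomy only, the sentence shows that absence of menses was not meant to be enough for them. Because the FSH clause is one more alternative and does not restrict the amenorrhea route, it stops binding once 12 months have passed since surgery.

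The primary endpoint is percentage change in serum estradiol, and section 1.1 asks whether less frequent dosing suppresses it as well as daily dosing. A woman whose ovaries still produce estradiol falls outside the population that the criterion is meant to define, and her change may reflect ovarian activity more than schedule. Once enrolled she stays in the analysis. She is eligible as written, section 13.6 includes all women irrespective of compliance, and the according-to-protocol subgroup removes only non-compliers.

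**Working it through.** **1. The logic of 4.1.1.** Describe each woman by five yes/no attributes: age 60 or over (A), no menses for at least 12 months (M), bilateral oophorectomy (B), hysterectomy (H), FSH in the menopausal range (F).

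- Literal rule: A, or M, or B, or (H and not B and F and not A).
- Rule that the FSH clause appears to intend: A, or B, or (M and not H), or (H and not B and F and not A).

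Over all 32 combinations the two rules differ in exactly one: under 60, no menses for at least 12 months, no bilateral oophorectomy, hysterectomy, and FSH not menopausal (or not tested). The literal rule admits her and the other does not. Within the first 12 months after surgery the literal rule still requires FSH, unless her menses had already stopped earlier.

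**2. Later safeguards.**

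- Sections 7.1 and 7.3: the FSH trigger is undefined, and under the literal list FSH is not needed for this woman.
- Section 4.2: no exclusion applies to her.
- Section 6.8: eligibility is verified at the site, confirmed by the site investigator and confirmed again by coordinating staff, but each step applies the same sentence.
- Baseline estradiol: stored for central measurement and not used for eligibility.

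**3. The plan's own sample size.** Section 13.4 gives the margin: "we assume a non-inferiority difference of 6% in percentage changes of estradiol after treatment from baseline". Its other inputs are SD 11, true difference 0, one-sided alpha 0.025 and 54 evaluable per arm.

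- Noncentrality = 6 / (11 × √(2/54)) = 6 / 2.117 = 2.83, with 106 degrees of freedom.
- Power from the noncentral t is 80.2%; with 53 per arm it is 79.4%. So 54 is the smallest number that reaches 80%.
- 162 / 0.90 = 180 randomised. The stated figures reproduce and are not in dispute.

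**4. Illustration of sensitivity.** Assumption, not in the documents: one such woman has 0% change where -80% is expected, a gap of 80 points.

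- Shift in arm mean = 80 / 54 = 1.48 points, a quarter of the 6-point margin (1.48 / 6 = 0.25).
- Arm SD = √(121 × 53/54 + 80² × 53/54²) = √(118.8 + 116.3) = 15.3.
- One in a low-dose arm, none in the daily arm: SE = √(121/54 + 235.1/54) = 2.57, and (6 - 1.48)/2.57 - 1.96 = -0.20, so power is about 42% by normal approximation. Simulating the t-test gives 39%.
- One in each compared arm: no net shift, SE = √(2 × 235.1/54) = 2.95, and 6/2.95 - 1.96 = 0.07, so power is about 53% by approximation and about 52% by simulation.
- One in the daily arm only: the shift favours the low dose. Simulated power rises to about 87%, and the false-positive rate at a true 6-point deficit rises from about 2.5% to about 4.5%.
- A milder case, -40% instead of 0% in a low-dose arm: simulated power about 65%.

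**The case against.** The best defence is that the specific clause governs the general one. The sentence names women with hysterectomy only and says what those under 60 need, and the conditional FSH entry in sections 7.1 and 7.3 has an obvious referent in that clause. A careful site would probably read it so. That reading is plausible, but it is not written. Five sites in two countries, using local FSH guidelines, need a rule that does not depend on it.

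A reader might infer that nothing checks eligibility before randomisation. Section 6.8 does not support that, since several confirmations are required. Their limit is only that they apply the ambiguous text.

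A reader might also infer that the route opens the trial to drug-induced or procedure-related amenorrhea in general. The wording is silent on cause, but such examples come from outside the documents. Section 4.2 already excludes earlier breast-cancer chemotherapy and endocrine therapy, recent systemic HRT and recent SERM use. This is a question for the sponsor, not a finding.

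On size, the objection largely stands. The 0% response is assumed, the 39% figure places the woman in a low-dose arm only, and it uses an unadjusted comparison of means. Section 13.4 also plans ANCOVA with baseline estradiol and possible confounders, a residual check with transformation if needed, and medians with interquartile ranges. Any of these could reduce the influence of one extreme value, although none of them makes her a member of the target population.

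**Conclusion.** The conflict in 4.1.1 is real and confined to one profile: under 60, hysterectomy only, at least 12 months without menses, and FSH not menopausal or not tested. The text as written admits her without the result that the same sentence names, and no later passage settles the matter. It should be corrected because it concerns who belongs in a trial whose primary endpoint is estradiol.

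The statistical consequence is conditional. The documents do not give the number of such women, which may be zero, nor their estradiol response. Under the stated assumption one woman in a low-dose arm would cut power of the unadjusted t-test from 80% to about 39%, and one in each compared arm to about 52%. These figures show how sensitive a 6-point margin with SD 11 is to a single unsuppressed value. A reader might take them as a forecast that the trial is underpowered; the documents do not support that. Nor do they tie the SD of 11% to a particular population, so it cannot be argued that the SD was derived for women without ovarian function.

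**What to change.** Reconcile the two clauses in 4.1.1 so that the amenorrhea route does not apply to women with hysterectomy only, and the document's own FSH clause governs those under 60. In footnote 5 of section 7.1 and in section 7.3, define when FSH is needed by reference to that clause. Ask the sponsor to confirm whether the amenorrhea route is meant to cover amenorrhea from other non-natural causes, and to say so in the text. No wider rewriting of the menopause definition is needed for this point.

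The cost is one amended sentence, two short cross-references and a few more FSH tests within a baseline panel that already lists FSH. There may be a few more screen failures. Some women under 60 whose menses stopped naturally before a hysterectomy would also need the test.
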